**Nasal Iodophor Antiseptic vs Nasal Mupirocin Antibiotic in the Setting of Chlorhexidine
Bathing to Prevent Infections in Adult ICUS: A Randomized Clinical Trial
NCT#: 03140423**

4/28/2017

Mupirocin-Iodophor Swap Out Trial - Protocol

Conduct a cluster-randomized non-inferiority trial comparing mupirocin vs iodophor for nasal decolonization of ICU patients on *S. aureus* clinical cultures and all-cause bloodstream infection in the setting of routine chlorhexidine bathing (Mupirocin-Iodophor Swap Out Trial).

1.1 Significance and Innovation

Intensive care units (ICUs) have one of the highest rates of healthcare-associated infections due the patients' severity of illness and frequent use of medical devices.^{1 2 3} We previously conducted a cluster-randomized trial of decolonization in adult ICUs (REDUCE MRSA Trial) in the Hospital Corporation of America (HCA) health system.⁴ We showed that ICUs using chlorhexidine (CHG) antiseptic for routine daily bathing and mupirocin antibiotic for nasal decolonization of all admissions experienced a 37% reduction in methicillin-resistant *Staphylococcus aureus* (MRSA) clinical cultures and a 44% reduction in all-cause bloodstream infection. Nasal mupirocin has been shown to be important because CHG does not clear the nasal reservoir of *S. aureus*, one of the most common and virulent healthcare-associated pathogens.^{5 6 7}

In response to the REDUCE MRSA Trial and other clinical trials,^{4 8 9} ICU decolonization has been adopted throughout HCA's ICUs and broadly across the United States. However, despite evidence showing that the combination of mupirocin and CHG is effective in reducing all-pathogen ICU infection as well as *S. aureus* carriage and infection,^{4 10 11 12} many hospitals outside HCA are omitting mupirocin due to concerns of eliciting mupirocin resistance. We found an increase in mupirocin resistance from 10% to 17% during the 18 month period of the REDUCE MRSA trial,¹³ and others have reported high rates of resistance in clinical settings.^{14 15 16 17 18 19}

Alternative agents that do not readily engender resistance to mupirocin but prevent infections are thus needed. This phenomenon of resistance emerging with use has been observed for many antibiotics. In contrast, antiseptics, such as alcohol, iodophor, and CHG, have not been shown to engender clinically meaningful resistance, likely due to their small molecular size.^{20 21 22 23 17 18 19 20 24} We did not identify CHG resistance in the REDUCE MRSA Trial,¹⁴ and prior studies evaluating antiseptics versus antibiotics for prevention of urinary tract infection or otitis media have found no evidence of antiseptic resistance.^{25 26} Of specific relevance to this study, iodophor resistance has not been reported despite over 50 years of use in healthcare and households.

In this aim, we evaluate the ability of a nasal antiseptic to perform similarly to mupirocin when used in combination with CHG for universal ICU decolonization. This trial will be the first large-scale comparison of intranasal antibiotic vs. antiseptic as components of a standard decolonization regimen with CHG. It will be conducted as a pragmatic comparative effectiveness trial in over 100 community hospitals, and thus have immediate applicability to the most U.S. hospitals.

1.2 Approach

1.2.1 Study Population

This trial is based in the HCA Healthcare (formerly Hospital Corporation of America) system, which is the largest private inpatient provider in the U.S., including over 168 hospitals across 23 states in the US and areas in the United Kingdom. Hospitals are predominantly community-based, although they range in size from small facilities to large complex tertiary medical centers. HCA supports an annual volume of 2 million US admissions and 8 million emergency department visits. Overall, 1 in 20 admissions in the U.S. occurs in an HCA facility.

The Mupirocin-Iodophor Swap Out trial will focus on the study population of patients in adult intensive care units (ICUs) in HCA hospitals. All U.S. HCA hospitals with an adult ICU will be eligible to participate. Exclusion criteria include ICUs with an average length of stay of less than 2 days, and HCA hospitals that are not able to transfer or merge data into the centralized data warehouse for the baseline and intervention periods of the study (e.g. newly-acquired hospital that lack baseline data or hospitals not using MEDITECH as an electronic health system platform). The latter exclusion only applies to a small number of facilities, mostly those who were newly-acquired.

1.2.2 Study Design

As mentioned above, the HCA health system adopted universal ICU decolonization for adult ICUs in response to the results of the REDUCE MRSA Trial. HCA corporate guidance to their hospitals espouses use

of twice daily nasal mupirocin for the first 5 days of an ICU stay and daily chlorhexidine bathing for the duration of the ICU stay. The corporate campaign launched in Spring of 2013 with high compliance adoption by July 2013. Subsequent HCA evaluations demonstrated a 24% reduction in health system ICU central line associated bloodstream infections attributable to universal ICU decolonization.²⁷

In this context, we will conduct a two-arm 18-month non-inferiority cluster randomized controlled trial of HCA hospitals, evaluating two regimens. Hospitals randomized to Arm 1 will be assigned to the mupirocin-based usual care regimen for adult ICUs in the HCA health system. This will involve universal decolonization for all admitted patients using ICU-wide daily bathing with 2% chlorhexidine cloths for the duration of the ICU stay plus topical intranasal mupirocin ointment (bilateral nares) for the first five days of the ICU stay. Hospitals will be provided with re-training of HCA’s corporate guidance for this regimen and adherence will be tracked. Half of participating hospitals (minimum sample size of 60 hospitals) will be assigned this arm. We anticipate an average of 1.75 adult ICUs per hospital, or at least 105 ICUs in this arm.

Hospitals randomized to Arm 2 will be assigned to the iodophor-based regimen for adult ICUs in the HCA health system. This will involve universal decolonization for all admitted patients using ICU-wide daily bathing with 2% chlorhexidine cloths for the duration of the ICU stay plus topical intranasal iodophor (10% povidone-iodine to bilateral nares) for the first five days of the ICU stay. Hospitals will be provided with re-training of HCA’s corporate guidance for CHG bathing plus new training for the use of nasal iodophor. Adherence will be tracked. Half of participating hospitals (minimum sample size of 60 hospitals) will be assigned this arm. We anticipate an average of 1.75 adult ICUs per hospital, or at least 105 ICUs in this arm.

Thus, both arms will implement some form of universal decolonization during the ICU stay. The protocol will involve discontinuation of the regimen upon ICU discharge, regardless of whether the full intervention therapy had been applied during the ICU stay.

Table 1. Mupirocin-Iodophor Swap Out Trial Design Characteristics and Outcomes

[figure not shown]
Study Design	Cluster-randomized non-inferiority clinical trial
Unit of Randomization	Hospitals (all ICUs in a hospital will be assigned to the same regimen*)
Study Population	Adult ICU patients in participating HCA hospitals
Inclusion Criteria	Hospitals with at least 1 adult ICU, stable infection prevention initiatives and products during baseline period, agreement to refrain from new initiatives conflicting with the trial
Exclusion Criteria	ICUs with mean length-of-stay of less than 2 days. HCA hospitals having an electronic health record other than MEDITECH.
Group Assignments Arm 1 (N=60 hospitals) Arm 2 (N=60 hospitals)	Routine care: ICU decolonization with daily CHG baths and mupirocin for 5 days, twice daily Intervention: ICU decolonization with daily CHG baths and iodophor for 5 days, twice daily
Study Period	24-Month Baseline Period (Retrospective Data): May 2015 – Apr 2017 4-Month Training and Phase In Period: May – Oct 2017 (not included in analysis) 18-Month Intervention Period: Nov 2017 – Apr 2019
Primary Outcome	ICU-attributable S. aureus clinical cultures (MRSA + MSSA)
Secondary Outcomes	ICU attributable MRSA clinical cultures; ICU-attributable all-cause bloodstream infection;

* patient-level data will be analyzed by hospital

This trial will be registered with Clinicaltrials.gov, following approval by the Harvard Pilgrim Health Care Institutional Review Board, but prior to intervention launch.

Randomization will occur on the hospital level. All adult ICUs in a given hospital will be assigned to the same regimen (Figure 1).

Figure 1: Study Arms of Mupirocin-Iodophor Swap Out Trial

1.2.4 Recruitment

HCA hospitals will be recruited by HCA staff using their usual infrastructure for seeking participants for system-wide quality improvement projects. In particular, recruitment will be performed under the direction of [name] (Medical Director, Infection Prevention), [name], MS (Director, Infection Prevention and Control), and [name], MBA RN (Asst Vice President, Laboratory, Infection Prevention, and Research), with the support of [name] MD PhD, Chief Medical Officer of HCA. HCA health system is divided into two Groups (National and American), which in turn are divided into geographic divisions. Recruitment will be encouraged by HCA Group Presidents and HCA Division leadership.

Hospitals recruited as participants will be provided with the trial design and a description of both arms of the study. They will agree to be randomized and to implement their assigned protocol. An attestation letter confirming commitment to the trial will be signed by the Chief Executive Officer of each participating hospital. We will use a centralized IRB structure with each participating hospital ceding to the Harvard Pilgrim Health Care IRB.

1.2.5 Randomization

Randomization will occur during Spring 2017 and participating hospitals will be notified. This will be done because of the requisite 3-5 month period to submit and schedule the approval of intervention protocols by relevant hospital committees which often meet monthly or quarterly. As per routine policy in all hospitals, no training or implementation activities may occur prior to obtaining requisite hospital committee approvals. This will allow approval to occur and appropriate training of staff to occur prior to the phase in period which will involve acquisition and introduction of intervention product.

[figure not shown]
While this study is one of the largest cluster-randomized trials of hospitals, simple randomization of 120 hospitals will not ensure balance of key variables by chance alone, and without care could even result in very unequal numbers of hospitals in each arm. Achieving balance on key features of the randomization units (in this case, hospitals) is a critical task in cluster-randomized trials, but little literature on it exists. Unlike individually-randomized trials, information about the clusters is often known in advance, but the number of clusters to be randomized can be relatively small. The existence of a priori data can mitigate the small numbers and help to obtain adequate balance through stratification or other methods. One attractive approach is to establish tuplets—matched sets (pairs, for a two-arm trial) – in which one member of each tuplet is

assigned to each arm. Schemes for constructing tuples need not be guided by theory. A formal approach would be to calculate the Mahalanobis distance between hospitals across all key variables and choose the set of tuples with the minimum average distance. In this approach, we could standardize the variables, and then multiply by values calibrated to reflect any difference in the importance of balancing them. Other approaches are more ad hoc, such as prioritizing broad classes of balance on a key variable and making pairs within these strata based on lower-priority variables. However, there is no “best” method of tuple construction, only sets that come closer to meeting the varied needs of each trial.

We will use methods to inform the choice of tuple-construction scheme which we previously developed in the REDUCE MRSA trial. We will establish the pairs under several plausible tuple-construction schemes, and use graphical methods to compare all possible realizations for balance between the arms under each scheme. For example, if two variables were to be balanced, we would tentatively divide the sample into two groups under a tuple construction scheme and then generate a scatterplot showing the between-arm absolute value of the mean difference for one variable on the x-axis and the second on the y-axis for each possible result of the randomization. We would then divide the groups again under the same scheme, and find another point on the scatterplot. Repeating many times would show the typical and distribution of balance under a scheme. Comparing the resulting scatterplots from each tuple-construction scheme can reveal the relative risks of imbalance and benefits for balance accruing to each randomization scheme, in a practical sense. One tuple construction method may result in generally close balance on one key characteristic and very variable balance on the other, while a competing scheme has good median balance on both characteristics, but where each has a long tail implying a few bad-luck assignments with poor balance.

We hope to consider balance on more than two factors, and for assessing the impact on balance in this case, we will use a parallel coordinates plot, a multivariate plot method. A simulated example is shown in Figure 2. There we show a potential result of a single tuple construction method. The variables shown are volume, baseline rate of an outcome, the baseline rate of chlorhexidine use, and baseline rate of bathing. Each blue, red, green, or black line shows the mean difference between arms for all four variables for one potential realized randomization. The results show that a few randomizations, in blue, are relatively imbalanced on volume and outcome but balanced on chlorhexidine use and bathing, while a few others, in black, have the reverse pattern. The green and red realizations are approximately equally balanced across these variables. If we considered it more important to balance on volume and outcome, this would probably not be an ideal scheme.

Figure 2.

As a final note, we could consider the relative costs and benefits of strata of four, rather than tuples, which are strata of two. There are sound statistical reasons to expect power to be slightly better with strata of four, although there is some debate on this point. However, the balance between the arms may be worse. The balance is of central importance, since balance ensures that the observed effect is not confounded—confounding requires that the confounder be out of balance between the arms. We will examine whether the

gain in power is strong enough, and the loss of balance slight enough, to pursue strata of four in place of triplets.

We will focus on balancing the baseline outcome values in participating hospitals, baseline adherence to the HCA guidance for universal decolonization with chlorhexidine and mupirocin, measures of case severity index, and ICU patient day volume. We will additionally consider accounting for demographics, and ICU length of stay.

1.2.6 Phase In Timeline

Trial implementation timeline is shown in Table 3.

Table 3. Implementation Timeline

Process	Timeline
Collect Baseline Data	Data collection, cleaning, and derivation of randomization variables and confirmation of power occurs Summer 2016-Spring 2017
Randomization	Randomization will occur in Spring 2017
Notification	Hospitals notified of randomization status to schedule the relevant hospital committees for approval
Committee Approvals	Jan-Mar 2017
Training	Prior to phase-in, coaching calls, training materials and computer-based training will be launched
Phase In Launch	May-October 2017: Implementation of nasal iodophor in intervention arm. Both arms: pharmacy tracking of nasal decolonization product and feedback reports
Intervention Period	November 2017 – April 2019

Both arms will be provided with training and coaching conference calls and study campaign materials (Table 4). All training and coaching scripts as well as intervention materials will be designed by the Steering Committee, which will meet weekly during the trial. Strategies will heavily favor mechanisms that utilize HCA's current infrastructure for performance improvement and quality improvement projects.

Table 4. Intervention Elements

Type of Element	Leader	Frequency/Comments
Coaching Conference Calls	Investigators	Monthly during intervention
Intervention Tool Kit		
Campaign flyers	Developed by Investigators/study staff	
Powerpoint materials	Developed by Investigators/study staff	
Instructional materials	Developed by Investigators/study staff	
Help line	HCA leaders, study staff	

All training calls will be led by study investigators, [name] (lead investigator) and [name] (site PI for HCA). Campaign materials will be disseminated at the start of the phase-in period, and will include an information packet as well as flyers and web-based information.

1.2.7 Implementation

Intranasal iodophor will be implemented in the intervention arm using an admission order set similar to the current HCA process for universal mupirocin. This arm will receive iodophor product and training during the Phase-In Period (Table 5). The routine care arm will receive refresher training for mupirocin and support for admission order processes during that period to ensure that differential compliance is not a driver of trial results. Both arms will receive refresher training in CHG bathing and processes.

Table 5. Mupirocin-Iodophor Swap Out Trial Protocol Training Materials

Protocol Training	Description
1. Computer Based Training	Arm-specific protocol training module required of all staff in participating units
2. Nursing Protocol	Nursing protocol for use of mupirocin vs. iodophor
3. Dos and Don'ts	Quick reference protocol guide
4. Patient Talking Points	Talking points for common patient questions about the assigned protocol
5. Frequently Asked Questions	Staff answers to common patient questions about the protocol
6. Huddle Training	Periodic refresher training on key protocol points
7. Just in Time Training	On-the-spot training and reference guide for temporary/float nurses
8. Study Related Events	Forms for reporting study related events (iodophor) and side effects (mupirocin)

Toolkit binders with trial instructions and protocols will be provided to each unit nursing and medical director, infection prevention program lead, nurse education team, and Chief Nursing Officer for each participating hospital in each arm.

Feedback on compliance will be provided to each hospital. Usual care hospitals will receive at least monthly compliance data on daily chlorhexidine bathing and use of nasal mupirocin. Iodophor-CHG hospitals will receive at least monthly compliance feedback on daily chlorhexidine bathing and use of nasal iodophor.

Staff skills assessment forms (bathing observation checklist) will be used by peer nurses or the unit nursing director to ensure adherence to the assigned protocol. Nurses in HCA hospitals currently document bathing activities each shift. We will use this electronic documentation for compliance tracking of whether a CHG bath or shower was given. Compliance with nasal decolonization will be tracked through patient and unit-specific automated pharmacy reports for administration of either product. Compliance will be assessed and fed back to unit champions during twice-monthly coaching calls with a goal of 85% compliance, a level we have previously achieved in this population. Periodic maintenance reminders will be provided in both arms and will reflect common lapses identified by ongoing compliance assessments.

Study investigators will perform site visits as needed to various participating hospitals based upon requests for assistance, concerns about application of intervention protocols, or evidence of low compliance. These procedures are comparable to those used by HCA when implementing other Quality Improvement protocols. Oversight for the design and conduct of this trial will be provided by the Steering Committee (see above), which will meet weekly.

1.2.8 Nasal Iodophor

Nasal iodophor will be used for the nasal decolonization regimen for hospitals randomized to Arm 2 (Iodophor arm), using Clorox Nasal Antiseptic Swabs, a 10% povidone-iodine product. This product is FDA cleared for use in the nose and the manufacturer has released guidance for routine use for decolonization. Thus, the use of povidone-iodine swabs in the Swap Out Trial is to apply one swab in a circular motion to each nostril for 30 seconds, twice daily for 5 days.

Clorox Nasal Antiseptic Swabs has a separate set of directions for pre-operative nasal decolonization, which continues to use double the dose for a one-time application. Participating sites will be trained to ensure that they are aware of the differences in manufacturer guidance for routine ICU decolonization vs pre-operative indications which requires application of two swabs per nostril.

1.2.9 Likelihood of Study-Related Events

Regarding safety, we note that 10% iodophor has been the national standard of care for pre-surgical preparation for surgery for decades, including on mucous membranes of the nose and throat. It is also used for nasal decolonization prior to joint surgery, where it has been shown to be better tolerated than mupirocin.²⁸

The evidence for anaphylaxis for iodophor has been specifically related to contrast dye where an iodine-containing substance is injected directly into the bloodstream. This type of adverse event carries a 1% risk for direct injection into the bloodstream and is exceedingly rare in the use of iodophor for mucous membranes (so rare that estimates of frequency are not available).

In addition, as part of a pilot decolonization intervention study, povidone-iodine nasal antiseptic swabs were applied to residents in three southern California nursing homes for 6 months. Two swabs were applied in a circular motion to each nostril, twice daily for 5 days every other week (total of 13 weeks of application to residents). Accounting for facility census and protocol adherence, a total of 22,020 applications were administered across all three facilities without any adverse events reported.²⁹⁻³⁰ We note that this pilot involved a contributed product from 3M, which was 5% povidone iodine swabs (also FDA cleared for nasal use).

After the above pilot, as part of routine quality improvement, one of the nursing homes continued the use of nasal iodophor, but changed to a 10% povidone-iodine product (Clorox) and used one swab per nostril per application instead of 2 swabs per nostril per application. This was due to the fact that nursing staff felt that the two-swab-per-nostril regimen was redundant in application. Accounting for facility census and protocol adherence, a total of 1,987 applications were administered without any report of adverse events. Given the interest in a simpler regimen, we asked to evaluate whether the effect on nasal decolonization of *S. aureus* was similar between the prior 5% povidone-iodine two-swab regimen and the 10% one-swab povidone-iodine swab regimen. Nasal and skin cultures were taken from residents confirmed nearly identical reductions in MRSA with the 5% povidone-iodine two-swab regimen and the 10% one-swab povidone-iodine swab regimen.

1.2.10 Monitoring Study-Related Events

To monitor the occurrence of study-related events, a Study-Related Events Submission Form will be provided to Arm 2 facilities to document all events possibly related to use of iodophor, as part of study procedures. Clinical staff will be required to provide specific details regarding the event such as the body parts affected, the agent related to the event, a description of the reaction, and the corrective action that was taken to resolve the event. Clinical staff will be instructed to report all events to their designated nurse manager or director who will securely fax Study-Related Event Forms (iodophor). All clinical decision-making related to study related events will be at the discretion of the treating physician, not trial investigators or study staff, as is routine for quality improvement protocols.

Facilities will be asked to submit Study-Related Event Submission Forms as events are found. We will use our regular trial coaching calls to prompt facilities to report on schedule. Call attendance will be tracked. In the event that a facility is unable to attend, study staff will follow up to obtain a status update. A database will be used to document reported study-related events that take place in participating facilities. This tool will enable the project staff to closely track and assess any events deemed to be associated with the trial. The user will be able to document specific details regarding the event, and it will allow the user to keep a case open if the event is ongoing or close a case if the event is resolved.

Additionally, a Side-Effects Form for mupirocin-related events will be provided to Arm 1 facilities. Clinical staff at Arm 1 facilities will be asked to document and report all events possibly related to use of mupirocin, providing the same type of information as requested in the iodophor form. While nasal mupirocin is not part of the intervention, this information is requested so that the frequency and severity of mupirocin-related events can be compared to that of iodophor.

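### Prompting, follow-up and case tracking are stated only for the iodophor arm's event form, so the intended tolerability comparison may be biased against iodophor

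*Protocol*

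**What the plan says.** Protocol section 1.2.10 starts with the iodophor arm: "a Study-Related Events Submission Form will be provided to Arm 2 facilities to document all events possibly related to use of iodophor". It says of the form's content: "Clinical staff will be required to provide specific details regarding the event". On the chain of reporting it says: "Clinical staff will be instructed to report all events to their designated nurse manager or director". That manager or director then faxes the form, which the sentence labels as the iodophor form.

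The next paragraph begins with the same form: "Facilities will be asked to submit Study-Related Event Submission Forms as events are found". It continues: "We will use our regular trial coaching calls to prompt facilities to report on schedule". Call attendance is tracked, study staff contact any facility that misses a call, and reported study-related events go into a database in which a case can be held open or closed.

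Only then does the section turn to the mupirocin arm, which receives a separate Side-Effects Form: "Clinical staff at Arm 1 facilities will be asked to document and report all events possibly related to use of mupirocin". The type of information matches the iodophor form. The reason given for collecting it is "so that the frequency and severity of mupirocin-related events can be compared to that of iodophor".

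The SAP lists no safety outcome and no analysis of event reports.

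**The concern.** A comparison of reported event frequencies is fair only if an event has the same chance of being reported in each arm. Section 1.2.10 states a comparative purpose but sets out the steps that raise reporting (prompting, chasing, tracking) next to one arm's form only. If sites follow that reading, a difference in reported frequency mixes tolerability with reporting effort.

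Two features of the setting make this worth settling. First, staff know which product they use. Under section 1.2.2, mupirocin has been the system's routine since 2013, while iodophor comes with new training. Familiarity could plausibly lower reporting of minor mupirocin effects, in the same direction as the written asymmetry, though the documents do not measure this. Second, reports may be few. Section 1.2.9 cites 22,020 and 1,987 iodophor applications in nursing homes with no adverse event reported. With few reports, a handful of missed forms could shift the contrast.

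What is at stake is the tolerability statement, not the efficacy result.

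**Working it through.** **Step 1. Set the two arms side by side (section 1.2.10).**

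| Element | Arm 2, iodophor | Arm 1, mupirocin |
|---|---|---|
| Form | Study-Related Events Submission Form | Side-Effects Form |
| Event scope | All events possibly related to the product | Same |
| Form content | Specific details required | Same type of information |
| Reporting verb | Staff instructed; facilities asked | Staff asked |
| Routing | Nurse manager or director, then fax | Not stated |
| Prompt on coaching calls | Stated in the paragraph on this form | Not stated |
| Follow-up of missed calls | Stated in the same paragraph | Not stated |
| Case database | Stated for study-related events | Not stated |

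Scope and content match. The differences that could change capture are in the last four rows.

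**Step 2. Does the term for the form cover both arms?** Table 5 in section 1.2.7 separates the terms by product: "Forms for reporting study related events (iodophor) and side effects (mupirocin"). Section 1.2.10 also describes mupirocin as outside the intervention. In the protocol's own vocabulary, study-related events are therefore iodophor events, and the database, which is defined by that term, most naturally holds iodophor events.

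**Step 3. Does anything extend the prompting to Arm 1?** The prompting paragraph speaks of facilities and participating facilities without naming an arm. Section 1.2.6 gives coaching calls to both arms, and Table 5 lists both forms among the training materials. Arm 1 could therefore have been prompted, but no sentence says so.

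**Step 4. Size.** There is no plan figure to reproduce: the documents give no capture rates and no expected event rates. Let p2 and p1 be the true risk per exposed patient in Arms 2 and 1, and c2 and c1 the share of events reported. Then

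apparent ratio = (p2 × c2) / (p1 × c1).

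With equal true risk (p2 = p1) this reduces to c2 / c1. The true ratio that would appear as 1.0 is c1 / c2. The capture values below are assumptions for illustration.

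| c2 | c1 | Apparent ratio at equal risk | True ratio that would appear as 1.0 |
|---|---|---|---|
| 0.80 | 0.80 | 0.80/0.80 = 1.00 | 0.80/0.80 = 1.00 |
| 0.80 | 0.60 | 0.80/0.60 = 1.33 | 0.60/0.80 = 0.75 |
| 0.80 | 0.40 | 0.80/0.40 = 2.00 | 0.40/0.80 = 0.50 |

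The first row is the case of no shortfall, and the documents do not rule it out. The last column shows the practical effect of a shortfall: a real tolerability advantage for iodophor could be hidden. Section 1.2.9 cites evidence that patients tolerate iodophor better, so this is the direction in which the sponsor might expect a difference.

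**The case against.** The strongest reply is that this is an unclear paragraph, not a biased design.

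- **Obligation.** A reader might contrast required in Arm 2 with asked in Arm 1 and infer a weaker duty for mupirocin. The text does not support that. Required governs the detail on the form, which Arm 1 matches, and facilities submitting the iodophor form are also only asked. What remains is that Arm 2 staff are instructed to report up the line, which is thin evidence on its own. I place no weight on this contrast.
- **Active against passive.** A reader might infer that iodophor events are actively solicited and mupirocin events only passively received. That goes too far. Both arms rely on staff completing a form, neither describes systematic questioning of patients, and the prompting paragraph is not expressly limited to Arm 2.
- **Planned use.** The protocol says frequencies can be compared, not that they will be. Event reports are not an outcome in Table 1 or in the outcomes table of section 1.2.11, and the SAP specifies no safety test, estimate or margin. At most a descriptive comparison is affected.
- **Direction.** Any shortfall in Arm 1 counts against the new product, so it would not conceal an iodophor harm.

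All four limit the point. They do not remove it. The comparison is the only reason given for collecting the Arm 1 reports, and matching form content governs what is written once a form is started, not whether one is started. At best the text is ambiguous on what the comparison depends on, across at least 120 hospitals.

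**Conclusion.** The point holds as a risk of differential reporting. The protocol ties routing, prompting, follow-up and case tracking by wording or position to the iodophor form, states none of them for the mupirocin form, and still intends the two sets of reports to be comparable. On the natural reading, capture may be lower in Arm 1, and the descriptive tolerability comparison may then be biased against iodophor.

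A reader might go further and conclude that the comparison is biased, or that iodophor will look worse by a known factor. The documents support neither: they do not show that a shortfall exists. The ratios of 1.33 to 2.0 rest wholly on assumed capture of 80% against 60% to 40%, and the value is 1.0 if capture is equal.

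The primary and secondary outcomes are drawn from the corporate data warehouse (section 1.2.11) and do not depend on these forms. This is an inexpensive improvement to the safety reporting, not a threat to the non-inferiority conclusion.

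**What to change.** 1. In section 1.2.10, state that the nasal-product event forms in both arms share the same reporting instruction, routing, coaching-call prompt, missed-call follow-up and database. A single form for events possibly related to the assigned nasal product would do this most simply.
2. Report events per exposed patient by arm. The pharmacy data already planned in section 1.2.12 cover both products by patient and can supply the denominators.
3. If handling differed between arms, present events descriptively by arm, state the difference as a limitation, and drop the between-arm comparison. The SAP notes that it was updated after the trial was completed. For data already collected, the remaining step is therefore to document how Arm 1 reports were obtained and, if that differed, to apply this item.

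The cost is protocol and form wording plus slightly more paperwork for Arm 1 hospitals. Both arms already have coaching calls, so no new contact with sites is needed.
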